Objective(s), primary and secondary	
Primary objectives:
 
 1. To demonstrate that SPINERY RF device is effective in short-term (3 months) pain reduction in patients affected by metastatic bone tumors involving the vertebral bodies, sacrum, iliac crest and peri-acetabulum with indication for standard therapy and in patients who have failed, not candidates or refuse standard therapy; 2. To demonstrate that SPINERY RF device is safe in the RF ablation treatment of metastatic bone tumors, without causing device-related adverse events including, in particular, nerve injury; 
Secondary objectives:
 
 1. To demonstrate that SPINERY RF device is effective in long-term (up to 12 months) pain reduction in patients affected by metastatic bone tumors in the areas of vertebral bodies (thoracic and/or lumbar), sacrum, iliac crest and peri-acetabulum; 2. To demonstrate safety in relation to usability; 3. To demonstrate the procedural performance in terms of a short learning curve.
Hypotheses, primary and secondary	
Primary hypothesis:
 
 - BPI Brief Pain Inventory scale performance in terms of palliative treatment: 
H0: $\mu_c = 0$
 
HA: $\mu_c \neq 0$
 
Where μ_c is the mean change from baseline to the 3-month visit in worst-pain score.
 
No formal hypotheses for the remaining objectives.

Risks and anticipated adverse device effects to be assessed	Risks of innovative device SPINERY are the same of the state-of-the-art technology: 
 - Carbonization - Post-operative pain

	
 - Limited/uncomplete treatment due to anatomical peculiarities - damage to surrounding tissue through iatrogenic injury - Nerve injury including thermal injury, puncture of spinal cord or nerve roots potentially resulting in radiculopathy, paresis, and paralysis - Pulmonary embolism - Hemothorax or pneumothorax - Infection - Unintended puncture - Hemorrhage - Hematoma
Design of the clinical investigation	
Clinical development stage	
Pivotal confirmatory.
 
Justification: pre-market study for demonstration of conformity of the device with the Essential Requirements for CE-marking.

Design type	Prospective, Single arm, Multicenter
Control group	No control group

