Comparator (control device or treatment)	No comparator, on the other hand the clinical outcomes of this palliative treatment will be compared with the clinical data obtained with similar devices in similar clinical conditions.
Measures to minimize/avoid bias	
 - New technology bias is minimized through an adequate training to the Medical Operator - Low statistical bias is minimized through an adequate estimate of the number of patients in the treatment group as compared to the state of the art - Multicentric study to minimize usability bias
Primary endpoint(s)	
 - Change of Worst Pain Score expressed as average reduction of 2 BPI (Brief Pain Inventory) scores: Thoracic/Lumbar/ Peri-acetabulum/Iliac Crest/Sacrum RF Ablation [Time Frame: Baseline, 3 months]. 
Change in pain will be calculated as:
 $\mu c = \text{worst-pain 3-month} - \text{worst-pain baseline}$ 
A negative average value for change in pain represents a lowering of the subject's pain score (an improvement, or reduction in pain) and a positive value represents an increase in the subject's pain score (a worsening or increase in pain).
 
Worst pain score at the target treatment site will be collected from the BPI in the past 24 hours.
 
 - Completion (%) of the ablation procedure without device-related adverse events including in particular nerve injury [Timeframe: Post-procedure, 3 months]. 
All the analyses will be performed according to ITT and PPT principle.

Secondary endpoint(s)	
 - Change of Worst Pain Score: Thoracic/Lumbar/ Peri-acetabulum/Iliac Crest/Sacrum RF Ablation [Time Frame: 1 month, 12 months]. Worst pain score at the target treatment site will be collected at each timepoint from the Brief Pain Inventory (BPI) in the past 24 hours. - Usability endpoint: Technical success (ability to perform access to treatment site and perform ablation) and procedural success (ability to perform access to treatment site and perform ablation for one or more complete cycles as planned by the physician) without product specialist intervention [Timeframe: Post-procedure]; - Procedural endpoint: procedure time, number of procedural errors, number of procedural and technical success for the same surgeon [Time Frame: Post-procedure]; 
All analyses will be performed according to ITT and PPT principle.

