Sample Size	52 subjects in a maximum of 10 sites
Follow-up	Baseline, Intra Procedure, Post procedure (within 24 hours), 1 month, 3 months and 12 months.
Duration of the clinical investigation	
Upon obtaining informed consent, each subject will complete an Enrollment/Baseline visit, SPINERY procedure visit (Day 0), prior to discharge (within 24 hours), 1 month and 3 months clinic visits), and a final post-procedure study visit (12 months) for a total of 5 study related visits.
 
The estimated time needed to enroll all subjects is approximately 6 months. The estimated time needed to obtain the CE Mark due to safe endpoints is 9 months (6 months for enrollment plus 3 months follow-up).
 
The overall study duration, from first subject enrollment to last subject visit (including 12-month follow-up), is expected to last approximately 18 months. The completion of the study is defined as the approval of the Final Study Report and closure of all sites.

Inclusion criteria	
 1. Patients with painful metastatic malignant lesions involving bone; 2. Patients, candidates to standard therapy, in which the RF ablation can be performed in combination with the Standard Therapy in accordance with the Investigator's indications; 3. Patients who have failed, not candidates or refuse Standard Therapy (chemotherapy or radiotherapy); 4. Patients with metastatic tumor size compatible with the expected ablation dimensions as reported for SPINERY devices in the IFU;

	
 5. Patients with localized pain resulting from not more than two sites of symptomatic metastatic disease 6. Patients that do not have evidence of impending fracture 7. Patients with metastatic lesions targeted for treatment located in the thoracic and/or lumbar vertebral body(ies), peri-acetabulum, iliac crest, and/or sacrum - no restrictions on location of lesion; 8. Patients with BPI-Report worst pain score $\geq 4/10$ at the target treatment site within the past 24 hours 9. Patients with Karnofsky score ≥ 40 at enrollment 10. Patients willing and able to provide a signed and dated informed consent, comply with the study plan, follow up visits and phone calls 11. Patients at least 18 years old at the time of informed consent

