4.2. Secondary Objectives

- To demonstrate that SPINERY RF device is effective in long-term (12 months) pain reduction in patients affected by metastatic bone tumors in the areas of vertebral bodies (thoracic and/or lumbar), sacrum, iliac crest and peri-acetabulum.
- To demonstrate safety in relation to usability;
- To demonstrate the procedural performance in terms of a short learning curve.

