5.2. Secondary Endpoints

- Change of Worst Pain Score: Thoracic/Lumbar/ Peri-acetabulum/Iliac Crest/Sacrum RF Ablation [Time Frame: Baseline vs. 1 month and 12 months];

Worst pain score at the target treatment site will be collected from the Brief Pain Inventory (BPI) in the past 24 hours.

- Usability endpoint: Technical success (ability to perform access to treatment site and perform ablation) and procedural success (ability to perform access to treatment site and perform ablation for one or more complete cycles as planned by the physician) without product specialist intervention [Timeframe: Post-procedure];
- Short learning curve endpoint: procedure time, number of procedural errors, number of procedural and technical success for the same surgeon [Time Frame: Post-procedure];

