6. TRIAL DESIGN

6.1. Summary of trial design

This is a prospective, single arm, uncontrolled multicenter study to assess the safety and effectiveness of SPINERY RF device in reducing pain in adult patients affected by metastatic bone tumors.

The trial design was defined in order to provide information regarding the clinical benefit of pain reduction; this clinical benefit is obtained thanks to the clinical performance of the device to provide coagulation and ablation.

Upon obtaining the informed consent, each subject will complete an enrollment/baseline visit, followed by treatment with SPINERY RF (Day 0); patients will then be visited immediately after the procedure (prior to hospital discharge within 24 hours), and after 1 month, 3 months and 12 months from the procedure, for a total of 5 study related visits.

The estimated time needed to enroll all subjects is approximately 6 months. The estimated time needed to obtain the CE Mark due to safe endpoints is 9 months (6 months for enrollment plus 3 months follow-up).

The overall study duration, from first subject enrollment to last subject visit (including 12 month follow-up), is expected to last approximately 18 months. The completion of the clinical study is defined as the approval of the Final Study Report and closure of all sites. Nevertheless, Clinical Study Reports at completion of each follow-up timeframe are expected in order to evaluate the evolution of the clinical study in relationship to the safety, the occurrence of clinical events and accomplishment of the Study Endpoints.

The following Clinical Study Reports will be issued during the clinical Study:

1. At completion of each planned study timeframe for all patients:
 - a. Postoperative, at achievement of primary safety endpoint;
 - b. 1 month, at achievement of the first timeframe of the secondary endpoint concerning the change of worst pain score;
 - c. 3 months (the primary endpoint) for CE mark purposes, at achievement of primary efficacy endpoint;
 - d. 12 months at achievement of the second timeframe of the secondary endpoint concerning the change of worst pain score;
2. In case of request from Ethical Committees or Competent Authority.

Planning of the Clinical Study Reports is summarized in the following table:

Timeframe of analysis	Endpoint	Expected clinical report content
-----------------------	----------	----------------------------------

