8.2.3. Specific Adverse Device Effect (ADE)

The following ADE should be carefully assessed as they are recognized as possible ADE for SPINERY based on the state of the art of other medical devices:

- Carbonization
- Post-operative pain
- Limited/uncomplete treatment due to anatomical peculiarities
- Damage to surrounding tissue through iatrogenic injury
- Nerve injury including thermal injury, puncture of spinal cord or nerve roots potentially resulting in radiculopathy, paresis, and paralysis
- Pulmonary embolism
- Hemothorax or pneumothorax
- Infection
- Unintended puncture
- Hemorrhage
- Hematoma

Unanticipated adverse device effects can occur. If they do occur, they will be handled as discussed in paragraph 8.1.3.

Aside from the risks listed above, there are no known gender-specific risks associated with the use of the SPINERY device. Minimization of the risks will be accomplished by selection of patients who are appropriate candidates for this device and by careful selection of Investigators and centers that have appropriate experience with this type of procedure. Also, intervention techniques, peri-interventional and post-interventional, will be those that are typically used in each study center.

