10.4. Clinical Study Reports

Clinical study reports will be issued at the completion of the following timeframes on all patients:

- Postoperative, at achievement of primary safety endpoint;
- 1 month, at achievement of the first timeframe of the secondary endpoint concerning the change of worst pain score;
- 3 months (the primary endpoint) for CE mark purposes, at achievement of primary efficacy endpoint;
- 12 months at achievement of the second timeframe of the secondary endpoint concerning the change of worst pain score (Final Clinical Report);

Statistical analysis will be performed at 1-month, 3-months and 12-months intervals on BPI worst pain score results and change as compared to baseline values.

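### The learning-curve objective cannot be assessed with the endpoint as specified: errors and successes are counted per surgeon, with no case order, denominator, analysis or criterion for 'short'

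*Combined protocol and SAP*

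**What the plan says.** The protocol lists as its last secondary objective (section 4.2, repeated in the synopsis) "To demonstrate the procedural performance in terms of a short learning curve". The matching endpoint in section 5.2 is "Short learning curve endpoint: procedure time, number of procedural errors, number of procedural and technical success for the same surgeon", assessed after the procedure. The synopsis gives the same components under another label: "Procedural endpoint: procedure time, number of procedural errors, number of procedural and technical success for the same surgeon".

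Technical and procedural success are defined under the usability endpoint in section 5.2. Procedural error is not defined anywhere, and neither is 'short'. The documents give no case sequence, no minimum caseload and no number of surgeons.

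On analysis, the synopsis says "No formal hypotheses for the remaining objectives". Section 10.4 says "Statistical analysis will be performed at 1-month, 3-months and 12-months intervals on BPI worst pain score results" and mentions no analysis of procedural data. The report plan in section 6.1 (Table 2) covers device-related adverse events and worst pain only.

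The synopsis gives the size as "52 subjects in a maximum of 10 sites". Operators are trained in advance (section 10.3), and section 8.2.3 refers to "careful selection of Investigators and centers that have appropriate experience with this type of procedure".

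**The concern.** Learning shows as a trend over an operator's consecutive cases. Two of the endpoint's three components are counts per surgeon. A count mixes the rate per case with the number of cases, and it discards order. Procedure time is a per-case measure and could show a trend, but the plan does not say that it will be set against case number.

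Procedure time also depends on things other than experience. Cementoplasty after ablation is optional (section 7.1), and needle type and combination are left to the physician (section 6.4.3). If case mix drifts over the study, time can change without learning.

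At stake is a statement about ease of adoption in the file for CE marking. Followed as written, the plan would report totals per surgeon that reflect who treated most patients, with no agreed way to say whether a short curve was shown.

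**Working it through.** **1. The plan's own sizing.** Section 10.2 uses SD 3, correlation 0.3, difference 2, two-sided alpha 0.05 and power 0.90. The SD of the change is 3 × √(2 × (1 − 0.3)) = 3.550. A paired t-test then needs 36 (power 0.908 at 36, 0.899 at 35), and 36/0.70 = 51.4, rounded up to 52. The figure reproduces, but it was set for pain and says nothing about learning.

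**2. What the counts measure.** Take two surgeons with the same constant success rate, 80% for illustration. With eight cases the expected number of successes is 8 × 0.8 = 6.4; with two cases it is 2 × 0.8 = 1.6. The counts differ fourfold with no learning in either. Conversely, a surgeon with errors in cases 1 and 2 of five and a surgeon with errors in cases 4 and 5 both score two errors, although their trends are opposite.

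**3. Cases available.** 52/10 = 5.2 per site at the ceiling, 52/5 = 10.4 at five sites, 52/4 = 13 at four. If two surgeons operated at each of 10 sites (an assumption), the figure would be 52/20 = 2.6 per surgeon.

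**4. Precision for procedure time, if case order were used.** Assumptions: equal caseloads, one common linear slope of log time on case number, a separate intercept per surgeon, no case-mix effect, and a coefficient of variation (CV) of 30-40% taken as the within-surgeon SD of log time. The documents give no such SD. With S surgeons and m cases each:

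- Sxx = sum of squared deviations of case numbers 1 to m (10 for m = 5; 82.5 for m = 10; 182 for m = 13)
- SE of slope = CV/√(S × Sxx)
- df = S × m − S − 1
- half-width of the first-to-last change = (m − 1) × t(0.975, df) × SE

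One surgeon, five cases: 4 × 3.182 × 0.30/√10 = 1.21, and with 0.40 it is 1.61.
Ten surgeons, five cases each: 4 × 2.023 × 0.30/√100 = 0.24, and with 0.40 it is 0.32.

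| Surgeons × cases | df | Half-width, log scale (CV 30% to 40%) | As a ratio |
|---|---|---|---|
| 1 × 5 | 3 | 1.21 to 1.61 | ×/÷ 3.4 to 5.0 |
| 1 × 10 | 8 | 0.69 to 0.91 | ×/÷ 2.0 to 2.5 |
| 1 × 13 | 11 | 0.59 to 0.78 | ×/÷ 1.8 to 2.2 |
| 10 × 5 | 39 | 0.24 to 0.32 | ×/÷ 1.3 to 1.4 |
| 5 × 10 | 44 | 0.27 to 0.36 | ×/÷ 1.3 to 1.4 |
| 4 × 13 | 47 | 0.27 to 0.36 | ×/÷ 1.3 to 1.4 |

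At 10 × 5, an observed fall of 1 − exp(−0.24) to 1 − exp(−0.32), about 22% to 28%, would exclude no change. For 80% power the true first-to-fifth change must be about 1.16 SD, a fall of 1 − exp(−1.16 × 0.30) = 29% to 1 − exp(−1.16 × 0.40) = 37%. For one surgeon with five cases it must be about 5.4 SD.

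**5. Success.** For one surgeon, 5 successes in 5 cases has an exact 95% lower bound of 48%. A perfect split of two early failures and three later successes gives Fisher p = 0.10. Pooled, 25 early against 25 later cases at assumed rates of 80% and 95%, treated as independent, gives power of about 36%.

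**The case against.** The plan disclaims formal hypotheses beyond the primary one, so the objective is in effect descriptive and the word 'demonstrate' may be loose drafting. That stands in part, and it is a reason to keep the point small. But a descriptive objective still needs a measure that can describe learning, and counts without order or denominator cannot.

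The phrase about the same surgeon can be read as repeated measurement within each operator. If the procedure date (Day 0 for each subject, section 6.1) and the operator are on file, case order could be rebuilt. That also stands, conditionally: section 6.4.4 mentions a usability form, but the form is not in the documents and nothing confirms that the operator is captured. Even so, no analysis is laid down.

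Training and selection do not defeat the aim. Section 8.2.3 refers to experience with this type of procedure, not with this device, so learning among trained operators new to the device is a fair target.

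Two stronger readings are tempting. A reader might infer that 52 patients over up to 10 sites make the objective impossible. The documents do not support that: ten is a maximum, fewer sites give more cases each, and the pooled analysis of procedure time is workable at all three layouts in the table. A reader might also infer that any result would satisfy the objective. That goes too far, since times or errors that rose over successive cases could not fairly be called a short learning curve. What is true is that no criterion is stated.

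**Conclusion.** The point holds as a fault in how the endpoint is specified, not as a shortage of patients. As written, the endpoint cannot assess the objective: two of its three components track caseload, none is tied to case order, and there is no analysis or criterion.

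Curves for single surgeons would be uninformative at about five cases and still poor at 10 or 13. A pooled curve for procedure time is feasible; pooled success and error rates would be imprecise. These sizes rest on the assumed CV of 30-40%, equal caseloads, a common linear slope and an unstated number of surgeons, so they are illustrative. The finding about counts and missing order rests on none of them.

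This is a minor point on the last-listed secondary objective. The primary endpoints, their analysis and the sample size are untouched.

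**What to change.** 1. Record an operator code and the procedure date or consecutive case number on the usability form, if they are not already there, and define procedural error.
2. Add a short analysis paragraph to section 10: regress log procedure time on consecutive case number within operator, pooled over operators with an operator effect. Adjust for cementoplasty, which section 7.1 says is collected, and for other procedure features only if they are recorded and 52 procedures can support it.
3. Replace the counts by errors per case and by technical and procedural success as proportions, by case order (for example early against later cases), with confidence intervals. State that these will be imprecise and that later cases come only from the busier operators, so case order and operator are partly confounded.
4. Reword the objective in the synopsis and section 4.2 as estimating the change in procedural performance with case number among trained operators, and use one label for the endpoint in the synopsis and section 5.2.

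The cost is two fields on an existing form and some text, with no extra patients, visits or staff. The sponsor gives up the claim to demonstrate a short curve. The change is best made before enrolment, because operator and order may be hard to recover later.

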6. TRIAL DESIGN

6.1. Summary of trial design

This is a prospective, single arm, uncontrolled multicenter study to assess the safety and effectiveness of SPINERY RF device in reducing pain in adult patients affected by metastatic bone tumors.

The trial design was defined in order to provide information regarding the clinical benefit of pain reduction; this clinical benefit is obtained thanks to the clinical performance of the device to provide coagulation and ablation.

Upon obtaining the informed consent, each subject will complete an enrollment/baseline visit, followed by treatment with SPINERY RF (Day 0); patients will then be visited immediately after the procedure (prior to hospital discharge within 24 hours), and after 1 month, 3 months and 12 months from the procedure, for a total of 5 study related visits.

The estimated time needed to enroll all subjects is approximately 6 months. The estimated time needed to obtain the CE Mark due to safe endpoints is 9 months (6 months for enrollment plus 3 months follow-up).

The overall study duration, from first subject enrollment to last subject visit (including 12 month follow-up), is expected to last approximately 18 months. The completion of the clinical study is defined as the approval of the Final Study Report and closure of all sites. Nevertheless, Clinical Study Reports at completion of each follow-up timeframe are expected in order to evaluate the evolution of the clinical study in relationship to the safety, the occurrence of clinical events and accomplishment of the Study Endpoints.

The following Clinical Study Reports will be issued during the clinical Study:

1. At completion of each planned study timeframe for all patients:
 - a. Postoperative, at achievement of primary safety endpoint;
 - b. 1 month, at achievement of the first timeframe of the secondary endpoint concerning the change of worst pain score;
 - c. 3 months (the primary endpoint) for CE mark purposes, at achievement of primary efficacy endpoint;
 - d. 12 months at achievement of the second timeframe of the secondary endpoint concerning the change of worst pain score;
2. In case of request from Ethical Committees or Competent Authority.

Planning of the Clinical Study Reports is summarized in the following table:

Timeframe of analysis	Endpoint	Expected clinical report content
-----------------------	----------	----------------------------------

Postoperative	Primary safety endpoint	Number of device-related adverse events observed
1 month	First secondary endpoint at the first timeframe (1 month)	Data on change of worst pain score after 1 month from the procedure
3 months	Primary efficacy endpoint	Data on change of worst pain score after 3 months from the procedure
12 months - Final Clinical Report	First secondary endpoint at the second timeframe (12 months)	Data on change of worst pain score after 12 months from the procedure

Table 2 - Clinical Report Plan

